10.5.5 Solicited AEs

For the Solicited AE analysis, data collected on both the eDiary (*Solicited Adverse Event*) and the CRF (*Local/Systemic Reactogenicity*) will be summarised together using the maximum reported intensity grade from either source.

Post-vaccine assessments on the day of the first vaccination and up to and including 7 days post-vaccination will be summarised under the First vaccination, and post-vaccine assessments on the day of

the second vaccination and up to and including 7 days post-vaccination will be summarised under the Second vaccination. This is the 7-day reactogenicity period. Pre-vaccine assessments for the first and second vaccination will not be included in the summaries and will be listed only.

The severity values will be mapped from the two sources as shown in Table 5. For erythema, induration, and fever, the eDiary values will be mapped to the intensity grades as described in Section 10.5.5.1.

Table 5 Solicited AE Severity

Severity	Solicited AE (eDiary) categories	Local/systemic reactogenicity (CRF) categories
Grade 0	0 – None	None
Grade 1	1 – No interference with activity	Mild
Grade 2	2 – Some interference with activity	Moderate
Grade 3	3 – Significant; prevents daily activity	Severe
Grade 4	4 – ER visit or hospitalisation	Life Threatening

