**Table 2 Overall Schedule of Assessments at Each Study Visit**

Visit/Call	Screen	Vaccination Clinic	Telephone Call	Clinic	Vaccination Clinic	Telephone Call	Clinic			End of Study / Early Discontinuation Clinic
Timepoint (window)	Day						Month			
	-42 to -1	0	1 (+1d)	7 (±1d)	28 (+2d)	29 (+1d)	35 (±1d)	3 (±7d)	6 (±7d)	9 (±7d)
Informed consent	X									
Baseline/eligibility variables										
Demographics	X									
Inclusion and exclusion criteria	X									
Height and weight	X									
Medical and disease history	X									
HIV, HCV, HBV (quantitative HBV DNA and quantitative HBsAg), HDV serology	X									
Urinalysis	X									
Urine drug screen	X									
Urine pregnancy test (β-hCG)	X	X [a]			X [a]			X [f]	X [f]	X
Laboratory eligibility and safety tests										
Haematology	X	X [a]		X	X [a]		X	X	X	X
Biochemistry	X	X [a]		X	X [a]		X	X	X	X
Liver function tests	X	X [a]		X	X [a]		X	X	X	X
Study vaccination										
Vaccination dose		X			X			X [g]		
Post-dose observation		X			X			X [g]		
Nivolumab dose (Group 3 only) [b]					X					
Other safety assessments										
Full physical examination	X	X [a]			X [a]			X [a]		X
Symptom-directed physical examination				X			X	X	X	
Vital signs	X	X		X	X		X	X	X	X
Local/systemic reactogenicity		X [c]	X	X	X [c]	X	X	X [c]		
Unsolicited adverse events [d]	X	X	X	X	X	X	X	X	X	X
Serious adverse events and adverse events of special interest	X	X	X	X	X	X	X	X	X	X
Prior and concomitant medications	X	X	X	X	X	X	X	X	X	X
Blood for HBV disease markers [e]		X [a]		X	X [a]		X	X	X	X
Immunogenicity assessments										
Blood for cellular immunogenicity assessments		X [a]		X	X [a]		X	X [a]	X	X

[a] Pre-vaccination on Day 0, Day 28, and Month 3 (for UK participants having an MVA-HBV boost)

[b] Participants in Group 3 will receive nivolumab on Day 28. Group 4 is now closed. The patients will be observed for 30 minutes after vaccination. If there are no safety concerns (vital signs and reactogenicity), nivolumab will be infused over 30 minutes and the patients will be observed in the study centre for a further 30 minutes post-infusion.

[c] Captured pre-vaccination and post-vaccination on Days 0 and 28, and Month 3 (for UK participants having an MVA-HBV boost), via eDiaries for 7 days post-vaccination and then at the clinic assessment 7 days post-vaccination (Day 7 or 35)

[d] Recorded in the eCRF from the date the informed consent is signed, at all clinic visits to cover the period since the previous visit and during the visit

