## **6.2 Treatment Day Assessments (Day 0, Day 28 and Month 3 [MVA-HBV Boost (UK participants only)])**

The following will be performed pre-vaccination:

- Re-check of eligibility criteria (Day 0 only)
- A urine pregnancy test will be performed
- Blood samples will be taken for haematology, biochemistry and LFTs
- A full physical examination will be performed
- Vital signs (pulse rate, blood pressure and temperature) will be measured
- A baseline assessment of local and systemic reactogenicity will be performed (see [Appendix 1](#))
- Blood samples will be taken for immunogenicity assessments and HBV disease markers

Participants will then receive study vaccine by intramuscular injection in the non-dominant arm, and will be observed for 30 minutes post vaccination for safety concerns. Nivolumab will then be administered via an infusion, if applicable, according to [Table 1](#). All participants will be assessed in the clinic for at least 30 minutes post-vaccination and post-nivolumab infusion in case of immediate adverse events. The first participant in each cohort will be observed for 1 hour. In the first cohort, the second participant will not be dosed until 48 hours after the first sentinel participant.

The following will be performed post-vaccination:

- The vaccination site will be covered with a sterile dressing during the observation period; it will then be removed and disposed of as GMO waste
- Vital signs (pulse rate, blood pressure and temperature) will be measured at the end of the observation period
- Local and systemic reactogenicity will be assessed at the end of the observation period
- On Day 0, an eDiary, tape measure and thermometer will be provided to perform self-assessment of local and systemic reactogenicity for 7 days after the vaccinations. Participants will be reminded to do the following daily for the 7 days after each vaccination:
  - Take and record their temperature
  - Measure and record the size of vaccination site redness
  - Assess the other solicited adverse events listed in the eDiary

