#### 8.2.4.2 Assessment of Relationship

Solicited adverse events of vaccination site reactions will be considered causally related to study treatment.

For all other adverse events, the Investigator will determine a **causal relationship** to the study vaccine. A number of factors will be considered in making this assessment, including: 1) the temporal relationship of the event to the administration of the study vaccine 2) whether an alternative aetiology has been identified and 3) biological plausibility.

Causality of all adverse events should be assessed by the Investigator using the following question:

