***“Is there a reasonable possibility that the adverse event may have been caused by the study vaccine?”***

- **YES (related):** There is a reasonable possibility that the study vaccine contributed to the adverse event
- **NO (not related):** There is no reasonable possibility that the adverse event is causally related to the administration of the study vaccine. There are other, more likely causes and administration of the study vaccine is not suspected to have contributed to the adverse event

The Investigator is required to provide an assessment of relationship of AEs to the vaccine or study procedures and determines causality. The Sponsor and local medical monitor can add another causality assessment to the Investigator’s causality. However, the causality given by the Investigator must not be downgraded by the Sponsor or the local medical monitor. If the

Sponsor or the local medical monitor disagrees with the Investigator's causality assessment, the opinion of both the Investigator, the Sponsor and the local medical monitor should be provided with the report.

Every effort should be made by the Investigator to determine the existence of any pre-existing conditions (e.g. headache in adults or rashes in infants on study Day 0 with onset prior to study vaccination) that must be taken into consideration when assessing causal relationship of an adverse event. Pre-existing conditions should be recorded in the eCRF as baseline history and substantiated by appropriate source documentation. Intermittent conditions such as headaches may not be present on study Day 0 but may represent an adverse event if the intensity or duration of the event is worse than usual following study vaccine.

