10.5.5.1 Handling of Solicited AE (eDiary) data

Solicited adverse events are recorded in the eDiary for 7 days post-vaccination (Day 0 to Day 7, Day 28 to Day 35, and Month 3 to Month 3 + 7 days [only applicable for booster participants]). All solicited AEs are considered causally related to the study treatment.

Solicited local symptoms including pain, induration (swelling), warmth, and erythema (redness), and solicited systemic symptoms including feverishness, chills, myalgia (muscle ache), fatigue (tiredness), headache, nausea, arthralgia (joint ache), and malaise (a general feeling of unwell) will be reported in a standardised manner over a period of 7 consecutive days after vaccination.

These solicited AEs and their intensity grades are based on the Food and Drug Administration (FDA) Guidance on Toxicity Grading Scale as described in Appendix 1 of the Protocol. If induration (swelling) or erythema (redness) are recorded as < 25mm in diameter in the eDiary, then this will be categorised as no event (grade 0) for the purpose of analysis. Derived intensity grades for induration and erythema are done based only on the numeric value of the parameter assessed, and clinical signs and symptoms will not be considered.

In addition, oral temperature will also be recorded for 7 days post-vaccination. Fever is defined as oral temperature $\geq 38^{\circ}\text{C}$ and the intensity grades are derived as specified in Appendix 1 of the Protocol.

Solicited AEs with missing intensity will not be included in the 'Any' count of the respective solicited AE.

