12.7.2.2 Solicited Adverse Events

For each solicited symptom (grouped by local symptoms and systemic symptoms), the number and percentage of participants reporting an event will be summarised by vaccination (first vaccination, second vaccination) and overall.

For participants experiencing a solicited symptom (i.e. reporting a severity Grade 1 or higher), an additional summary of solicited symptoms by maximum severity after each vaccination (first vaccination, second vaccination) and overall will be presented.

Percentages for both analyses are based on the number of participants reporting the severity of any solicited symptom on any day within the 7-day reactogenicity period following each vaccination (as defined in Section 10.5.5).

Both analyses will be presented for the primary analysis and repeated for the sensitivity analysis (as defined in Section 10.10).

Solicited AEs, local and system reactogenicity, and diary body temperature will be listed separately. A combined listing including solicited symptoms from both the eDiary and CRF for the 7-day reactogenicity period will also be presented.

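### Solicited symptoms are counted without reference to the pre-dose grade, which inflates absolute reactogenicity rates, and the SAP's blanket causality rule contradicts the protocol undeclared

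*SAP*

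**What the plan says.** **Collection.** Protocol 6.2 lists, among the procedures before vaccination: "A baseline assessment of local and systemic reactogenicity will be performed". Footnote [c] to Protocol Table 2 describes the reactogenicity data as "Captured pre-vaccination and post-vaccination on Days 0 and 28".

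**Analysis.** SAP 10.5.5 pools eDiary and CRF grades for the seven days after each dose; they "will be summarised together using the maximum reported intensity grade from either source". On the grades taken before each dose it says: "Pre-vaccine assessments for the first and second vaccination will not be included in the summaries and will be listed only". SAP 12.7.2.2 tabulates each symptom by vaccination and overall, and takes Grade 1 or higher as experiencing the symptom. Neither section compares a post-dose grade with a pre-dose grade.

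**Causality.** SAP 10.5.5.1, which covers local and systemic symptoms alike, states: "All solicited AEs are considered causally related to the study treatment". Protocol 8.2.4.2 is narrower: "Solicited adverse events of vaccination site reactions will be considered causally related to study treatment". It leaves every other adverse event to the Investigator and describes pre-existing conditions, with headache as an example, as something "that must be taken into consideration when assessing causal relationship of an adverse event". SAP 6.1, which sets out the changes from the protocol, does not mention this one.

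**The concern.** Safety and reactogenicity are the primary objective. Every participant receives two vaccine doses, open label (Protocol 5.2.1 and 5.9), so no arm shows how often people with chronic hepatitis B on antivirals report fatigue, headache, myalgia, arthralgia or malaise in an ordinary week. The pre-dose grade is within-participant information on this, and the protocol already collects it. Under the SAP a participant whose mild fatigue is the same before and after a dose appears in the table exactly like one whose fatigue began after it. The published absolute rates would be too high by an amount that no summary reveals.

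The causality sentence is a second, separate matter. It replaces a judgement that the protocol assigns to the Investigator with an automatic rule for systemic symptoms, and a reader who relies on SAP 6.1 would not learn of it.

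**Working it through.** **Step 1. The plan's own figures.** The plan gives no background rate for any solicited symptom, so there is none to reproduce. Its one related figure (SAP 8.1) is an 80% chance of seeing an event of 10% incidence in 16 participants. This reproduces: 1 − 0.9^16 = 1 − 0.185 = 0.815. Only the group size of 16 is used below.

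**Step 2. The counting rule applied to one participant.** Suppose fatigue is Grade 1 before Day 0, after Day 0, before Day 28 and after Day 28.
- SAP rule (post-dose grade ≥ 1): counted after the first vaccination, after the second, and overall.
- New-or-worse rule (post-dose grade > pre-dose grade): 1 > 1 is false both times, so not counted.

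**Step 3. Who can be affected.** Protocol 4.3.1.1 allows vaccination during minor illness, but defers it for moderate or severe acute illness or a temperature above 37.5°C. The inflation therefore falls mainly on low-grade systemic symptoms. Local symptoms before dose 1 should be rare.

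**Step 4. Size, as an illustration.** Let b be the proportion with a given symptom before dosing that persists unchanged. This is an assumption; 5%, 10% and 20% are tried. With no vaccine effect, the expected count per symptom per dose is n × b, if all n participants contribute reports:

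| b | n = 16 (Groups 2 and 3, planned) | n = 9 (Group 4, SAP 8.1) |
|---|---|---|
| 5% | 0.8 | 0.45 |
| 10% | 1.6 | 0.9 |
| 20% | 3.2 | 1.8 |

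If the vaccine truly induces the symptom in a proportion v, independently of b, the reported rate is 1 − (1 − b)(1 − v). For v = 30%:
- b = 5%: 1 − 0.95 × 0.70 = 33.5%
- b = 10%: 1 − 0.90 × 0.70 = 37.0%
- b = 20%: 1 − 0.80 × 0.70 = 44.0%

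**Step 5. Carry-over from dose 1.** The first window closes on Day 7 and the second dose is on Day 28. A dose-1 symptom must last a further 28 − 7 = 21 days to be counted again under the second vaccination. This is possible but a minor part.

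**Step 6. The causality texts side by side.**
- Protocol 8.2.4.2: automatic for vaccination-site reactions; Investigator's judgement for the rest, weighing pre-existing conditions.
- Protocol 3.1.4: the individual stopping rule for Grade 3 systemic solicited events depends on a judgement of relatedness, so the protocol does not presume it.
- SAP 10.5.2: provides Investigator causality for unsolicited events only.
- SAP 10.5.5.1: all solicited events related.
- SAP 6.1: silent.

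For systemic solicited events the SAP and the protocol cannot both hold.

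**The case against.** The strongest reply is that the present tables are a normal descriptive summary and err towards over-reporting harm, which is the cautious direction in a first-in-human study of the combination. The pre-dose grades are listed, and in groups of 9 to 16 they can be read case by case. One clinic assessment is also a poor estimate of background for the highest grade over seven days. All of this stands. It is the reason to keep the present tables and to make the new-or-worse count supplementary. A listing, however, does not give a rate, and the reader would have to redo the analysis to obtain one.

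Several stronger readings are tempting but not supported:
- **That leaving out the pre-dose grades is itself a protocol departure.** The protocol collects them but nowhere promises a baseline-adjusted summary. Its text on pre-existing conditions instructs the Investigator; it is not an analysis rule.
- **That a combined row for any systemic event is inflated further.** SAP 12.7.2.2 specifies counts for each symptom, grouped as local or systemic, and names no such row.
- **That the blanket causality rule inflates the counts of related events.** The solicited tables are not split by relationship, and no document says that systemic solicited symptoms enter the related rows of SAP 12.7.2.1.
- **That restoring the protocol rule needs only a corrected sentence.** The documents do not show a causality field for eDiary symptoms. If none was captured, it would have to be judged afterwards in an open-label trial.

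SAP 16.0 lists a table of reactogenicity by vaccination and time point, which might have shown pre-dose results, but SAP 10.5.5 keeps pre-vaccine assessments out of the summaries.

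**Conclusion.** The point holds in two parts.

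First, the solicited-event tables overstate absolute rates of low-grade systemic symptoms by whatever share was already present and did not worsen. The size is unknown from the documents. Under an assumed 5% to 20% persisting unchanged it is 0.8 to 3.2 of 16 participants per symptom per dose, and full persistence is the upper case for each assumed rate. Comparisons between groups are less affected than absolute rates if background is similar across groups, although the groups are small and were opened in sequence (SAP 8.2). A reader might infer that carry-over from dose 1 seriously distorts the second-dose results; with 21 days between the end of the first window and Day 28, the documents do not support giving it that weight.

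Second, SAP 10.5.5.1 contradicts Protocol 8.2.4.2 on causality of systemic solicited events, and SAP 6.1 does not say so. This rests on the text alone and needs no assumption.

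**What to change.** 1. Keep the current tables in SAP 12.7.2.2.
2. Add, for each vaccination and group, the pre-dose prevalence of each solicited symptom.
3. Add a supplementary table that counts a symptom only when its post-dose grade exceeds the same participant's pre-dose grade for that symptom at that vaccination. State a rule for missing pre-dose grades, for example to count the event. Amend SAP 10.5.5 so that the pre-dose grades may be used in this way.
4. Report both tables when concluding on reactogenicity.
5. Reconcile SAP 10.5.5.1 with Protocol 8.2.4.2. Limit automatic relatedness to vaccination-site reactions, and use the Investigator's assessment for systemic solicited events where it was captured. Where it was not, declare the departure in SAP 6.1 and do not describe systemic solicited events as vaccine-related on the blanket rule alone.

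The cost is small: the added summaries come from symptom data already held, plus a short text change. The supplementary table omits a vaccine-induced symptom that only equals the pre-dose grade, which is why it should stand beside the existing table and not replace it.

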## 6 STUDY PROCEDURES AT EACH VISIT/SCHEDULE OF ASSESSMENTS

The study consists of the following:

- A 42-day screening period before the start of study treatment
- A study period of 9 months
- An end of study visit

The schedule of assessments at each visit is shown in [Table 2](#) and listed in [Section 6.1](#) to [Section 6.3.1](#). The study assessments are described in [Section 7](#).

**Note: any additional visits or assessments performed during the study e.g. to assess adverse events must also be recorded on the unscheduled procedures or unscheduled visits in the eCRF.**

Unsolicited adverse events will be recorded from the date the informed consent is signed and at all clinic visits, by questioning the participant at each visit whether they had any adverse events since the previous visit and by observing the participant during clinic visits.

Serious adverse events and AESIs will be recorded from the date the informed consent is signed until the end of the study and/or resolved or until participant contact discontinues.

Solicited AEs and medication taken to treat solicited AEs will be collected daily in the eDiary for 7 days post-vaccination.

All medications taken to treat unsolicited AEs and SAEs will be recorded in the eCRF by questioning the participant at each visit whether they took any concomitant medications since the previous visit.

Due to the COVID-19 pandemic, study centres will follow any local procedures in line with testing to ensure the safety of participants and staff.

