**A. Tables for Clinical Abnormalities**

Local Reaction to Injectable Product	Mild (Grade 1)	Moderate(Grade 2)	Severe (Grade 3)	Potentially Life Threatening (Grade 4)
Pain	Does not interfere with activity	Repeated use of non-narcotic pain reliever $\geq$ 24 hours or interferes with activity	Any use of narcotic pain reliever or prevents daily activity	Emergency room (ER) visit or hospitalization
Tenderness	Mild discomfort to touch	Discomfort with movement	Significant discomfort at rest	ER visit or hospitalization
Erythema/Redness *	2.5 – 5 cm	5.1 – 10 cm	$\geq$ 10 cm	Necrosis or exfoliative dermatitis
Induration/Swelling **	2.5 – 5 cm and does not interfere with activity	5.1 – 10 cm or interferes with activity	$\geq$ 10 cm or prevents daily activity	Necrosis

\* In addition to grading the measured local reaction at the greatest single diameter, the measurement should be recorded as a continuous variable.

\*\* Induration/Swelling should be evaluated and graded using the functional scale as well as the actual measurement.

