**Contains Nonbinding Recommendations**

Vital Signs *	Mild (Grade 1)	Moderate(Grade 2)	Severe (Grade 3)	Potentially Life Threatening (Grade 4)
Fever (°C) ** (°F) **	38.0 – 38.4 100.4 – 101.1	38.5 – 38.9 101.2 – 102.0	39.0 – 40 102.1 – 104	> 40 > 104
Tachycardia - beats per minute	101 – 115	116 – 130	> 130	ER visit or hospitalization for arrhythmia
Bradycardia - beats per minute***	50 – 54	45 – 49	< 45	ER visit or hospitalization for arrhythmia
Hypertension (systolic) - mm Hg	141 – 150	151 – 155	> 155	ER visit or hospitalization for malignant hypertension
Hypertension (diastolic) - mm Hg	91 – 95	96 – 100	> 100	ER visit or hospitalization for malignant hypertension
Hypotension (systolic) - mm Hg	85 – 89	80 – 84	< 80	ER visit or hospitalization for hypotensive shock
Respiratory Rate – breaths per minute	17 – 20	21 – 25	> 25	Intubation

\* Subject should be at rest for all vital sign measurements.

\*\* Oral temperature, no recent hot or cold beverages or smoking.

\*\*\* When resting heart rate is between 60 – 100 beats per minute. Use clinical judgement when characterizing bradycardia among some healthy subject populations, for example, conditioned athletes.

Systemic (General)	Mild (Grade 1)	Moderate(Grade 2)	Severe (Grade 3)	Potentially Life Threatening (Grade 4)
Nausea/vomiting	No interference with activity or 1 – 2 episodes/24 hours	Some interference with activity or > 2 episodes/24 hours	Prevents daily activity, requires outpatient IV hydration	ER visit or hospitalization for hypotensive shock
Diarrhea	2 – 3 loose stools or < 400 gms/24 hours	4 – 5 stools or 400 – 800 gms/24 hours	6 or more watery stools or > 800gms/24 hours or requires outpatient IV hydration	ER visit or hospitalization
Headache	No interference with activity	Repeated use of non-narcotic pain reliever > 24 hours or some interference with activity	Significant, any use of narcotic pain reliever or prevents daily activity	ER visit or hospitalization
Fatigue	No interference with activity	Some interference with activity	Significant, prevents daily activity	ER visit or hospitalization
Myalgia	No interference with activity	Some interference with activity	Significant, prevents daily activity	ER visit or hospitalization

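### SAP Table 5 grades diary pain and headache by activity alone, so Grade ≥2 and Grade ≥3 counts can fall below what protocol Appendix 1 would give

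*SAP*

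**What the plan says.** SAP 10.5.5 combines eDiary and CRF reactogenicity and takes the higher grade of the two. On severity it states: "The severity values will be mapped from the two sources as shown in Table 5". In that table, diary Grade 2 is "2 – Some interference with activity" and diary Grade 3 is "3 – Significant; prevents daily activity". Grade 4 is an emergency-room visit or hospitalisation. Three symptoms are handled separately: "For erythema, induration, and fever, the eDiary values will be mapped to the intensity grades as described in Section 10.5.5.1". Pain and headache are not among them, so they stay on Table 5.

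SAP 10.5.5.1 names the source of the scale: "intensity grades are based on the Food and Drug Administration (FDA) Guidance on Toxicity Grading Scale as described in Appendix 1 of the Protocol".

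For injection-site pain and headache, protocol Appendix 1 offers two alternative routes to Grades 2 and 3. Headache is Grade 2 for "Repeated use of non-narcotic pain reliever > 24 hours or some interference with activity"; pain at Grade 2 has the same form, with a threshold of at least 24 hours. Pain is Grade 3 for "Any use of narcotic pain reliever or prevents daily activity"; headache at Grade 3 also counts any narcotic use.

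The protocol collects the relevant data. Section 6 states: "Solicited AEs and medication taken to treat solicited AEs will be collected daily in the eDiary for 7 days post-vaccination". Section 5.10 says the same. The SAP does not use this record in grading, and SAP 6.1, which lists changes from the protocol, does not mention the omission.

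**The concern.** The SAP names a scale and then applies part of it. Someone whose pain or headache causes no interference because they have taken analgesics for two days is Grade 2 under Appendix 1 and Grade 1 under Table 5. Someone with some interference who takes one narcotic dose is Grade 3 under Appendix 1 and Grade 2 under Table 5. Since analgesics reduce interference with activity, the dropped criterion is the one that would catch treated symptoms.

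Reactogenicity belongs to the first primary endpoint, and the table of solicited events by intensity grade (14.3.2.27.a) is listed in SAP 16.0 for both the DMC and the interim analysis. SAP 10.5.5.1 says openly that induration and erythema are graded on the measurement only. It has no such statement for pain or headache, so a reader would assume that the full Appendix 1 rule was used.

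**Working it through.** The plan states no figure on this point, so there is none to reproduce. The check compares the two rules case by case.

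**Inputs.** Activity level and Table 5 grade: SAP 10.5.5. Pain-reliever criteria: protocol Appendix 1, rows for pain and headache. Group sizes: 16 planned for Groups 2 and 3 (protocol Table 1); 10 and 9 for Groups 1 and 4 (SAP 8.1).

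**Rule.** Table 5 grade = activity grade. Appendix 1 grade = the higher of the activity grade and the medication grade, because the criteria are joined by an either/or.

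| Activity | No qualifying analgesic | Repeated non-narcotic | Any narcotic |
|---|---|---|---|
| No interference | 1 vs 1 | **1 vs 2** | **1 vs 3** |
| Some interference | 2 vs 2 | 2 vs 2 | **2 vs 3** |
| Prevents activity | 3 vs 3 | 3 vs 3 | 3 vs 3 |
| ER visit or hospitalisation | 4 vs 4 | 4 vs 4 | 4 vs 4 |

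(Each cell: Table 5 grade vs Appendix 1 grade.)

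Three of the 12 combinations differ, and in all three Table 5 is lower. In none is it higher. Diary counts at Grade ≥2 and at Grade ≥3 can therefore err only downward. The count at exactly Grade 2 has no fixed direction, because the case of some interference plus a narcotic leaves Grade 2 for Grade 3.

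**Size per participant.** One re-graded participant changes a group rate by 1/n: 1/16 = 6.25 points, 1/10 = 10 points, 1/9 = 11.1 points. SAP 12.7.2.2 uses participants who report severity as the denominator, so the step is slightly larger if some do not report.

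**How far the CRF repairs this.** The higher-of-two-sources rule helps only if a CRF grade reflects the medication.
- On vaccination days, the clinic assessment comes at the end of the observation period (protocol 6.2), too early for 24 hours of analgesic use.
- Protocol Table 2 marks reactogenicity at the Day 1 and Day 29 calls, but section 6.3.1 describes those calls only as diary reminders.
- The next clinic grade is at Day 7 or Day 35, each with a window of one day either side. A visit 8 days after vaccination is allowed but lies outside the 7-day period in SAP 10.5.5.

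Pain or headache that is treated and gone before the 7-day visit may carry the diary grade only.

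**The case against.** The strongest reply has four parts.

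**An investigator route exists.** Protocol 8.2.4.1 directs grading to Appendix 1 where possible, section 5.10 has medication for solicited events discussed at clinic visits, SAP 10.5.5 takes the maximum of the sources, and SAP 10.10 prefers the CRF record when date and time coincide. This stands in part: some cases will be restored. The timing above shows why not all will be, and nothing in the SAP requires the visit grade to be revised in the light of the diary medication.

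**Table 5 may be shorthand.** Protocol 7.4.1.1 tells participants to grade by section 8.2.4.1, so the diary labels might abbreviate grades already assigned under Appendix 1. Table 5 does not support this: it gives the diary categories themselves, in activity terms.

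**The scale is only guidance.** The SAP says its grades are based on that scale, and an activity-only version is a defensible choice. That is fair, but it is a departure for these two symptoms and should be declared.

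**A medication upgrade can overshoot.** An analgesic taken for fever or myalgia must not raise the pain or headache grade. The protocol does not say that the eDiary records drug class, duration or the symptom treated. This stands and shapes the fix.

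A reader might also infer that severity in this trial is in fact understated, or that a plausible rate of analgesic use gives the loss in points. The documents do not support either inference: they report no analgesic use, and any such range would be pure assumption that ignores the CRF maximum.

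**Conclusion.** The point holds as a mismatch between the SAP and the scale it names, with a known direction and an unknown size. For injection-site pain and headache, diary-based counts at Grade ≥2 and Grade ≥3 can be too low and cannot be too high. This happens only when a participant meets a pain-reliever criterion above their activity grade and the CRF does not carry the higher grade. Each such participant is worth about 6 points in a group of 16, 10 in a group of 10 and 11 in a group of 9.

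Three limits apply. Grade ≥2 is not itself a primary threshold: the primary endpoint's severity cut is Grade ≥3, which changes only through narcotic use without prevented activity. The solicited severity tables are descriptive and sit under other safety endpoints (SAP 12.7.2). Other solicited symptoms are not touched by this point: myalgia and fatigue, for example, are activity-only in Appendix 1 as well.

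A reader might infer that the protocol 3.1.3 holding rules, which count Grade 3 solicited events, would be missed. The documents do not say that those rules are run on Table 5 grades, so that conclusion is not available.

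**What to change.** In SAP 10.5.5.1, define the analysed grade for pain and headache as the higher of the Table 5 grade and the Appendix 1 medication grade. Use only medication records (eDiary or concomitant-medication eCRF) whose recorded indication is injection-site pain or headache respectively. Let use on consecutive diary days stand for the Appendix 1 duration; this is an approximation, since a daily diary cannot separate 24 hours from slightly more. Show the Table 5-only grade alongside.

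If the records do not identify the symptom treated, keep Table 5 as the main grade, present the medication-based grade as an upper-bound sensitivity table, and declare the departure in SAP 6.1. This fallback may be needed: protocol 5.10 requires name, dates and indication on the concomitant-medication eCRF but does not describe the fields of the eDiary medication record.

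The cost is some coding of medication as narcotic or non-narcotic in a small trial, and slightly less favourable severity figures. No new data collection is needed. SAP 10.7 already codes medications to the WHO dictionary.
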